2.2 Study Description

The aim of this study is to observe the therapeutic effect of Baduanjin on improving physical fitness and bone density in MHD patients. A total of 50 MHD patients will be included and randomized into an intervention group of 25 cases and a control group of 25 cases. The intervention group undergo a 30 minute Baduanjin exercise under the guidance of a professional doctor before the dialysis day, including a 5-minute warm-up exercise, a 20 minute Baduanjin exercise, and a 5-minute relaxation exercise. The intervention group practice three days a week, while the control group maintain routine treatment and daily activities. Measure the indicators of each group at baseline, months 6, 12. The evaluation of physical fitness is based on the scores (which include muscle strength measurement; five-times sit-to-stand test; timed "up and go" test; sitting forward flexion test; standing on one-leg with eyes closed test). The bone mineral density test is based on the result of the double-energy DXA line. The quality of life score is based on the SF-36 score, and the emotional

score is based on the anxiety and depression scale.

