2.5 Statistical analysis, confidentiality plan

In terms of statistical analysis, SPSS 27.0 statistical software is used to establish a database and perform statistical processing. Descriptive statistical analysis, qualitative indicators are described as percentages, and quantitative indicators are described as mean \pm standard deviation. The data is subjected to normality testing and corresponding testing methods are adopted based on whether it follows a normal distribution. Qualitative data comparison adopts chi square test. Quantitative data conforms to normal distribution, t-test is used for comparison between two groups, and nonparametric test is used for abnormal distribution and $P < 0.05$ is considered statistically significant.

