2.6 Preservation and Confidentiality of Information

The researcher preserves all research data, including confirmation of all participants (able to effectively verify different record materials, such as hospital original records), all original informed consent forms with subject signatures, all case

[键入文字]

observation forms, detailed records of evaluation indicators, etc.

The results of this project may be published in medical journals, but we will keep the information of the subjects confidential in accordance with legal requirements. Unless required by relevant laws, the personal information of the subjects will not be disclosed. When necessary, research supervision and management departments, hospital ethics committees and their relevant personnel may access patient information in accordance with regulations.

3. Exit and Termination Criteria

1. patients with adverse reactions such as trauma, surgery or serious infection, cardiopulmonary failure, who cannot continue to perform exercise during the trial;
2. Patients who underwent kidney transplantation or disappeared or died for various reasons during the trial;
3. Patients with poor compliance during the trial, unwilling to continue to exercise or requesting to withdraw from the trial for various reasons.

4 Ethical issues

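### Section 3 makes poor compliance and stopping exercise reasons to exit; these exits fall mainly on the Baduanjin arm, with no stated follow-up or as-randomised analysis, so the comparison may be biased toward Baduanjin

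*Combined protocol and SAP*

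**What the plan says.** Section 2.2 describes 50 patients "randomized into an intervention group of 25 cases and a control group of 25 cases". The arms have different duties: "The intervention group practice three days a week, while the control group maintain routine treatment and daily activities". The schedule is a single sentence: "Measure the indicators of each group at baseline, months 6, 12".

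The exit rules stand under the heading "3. Exit and Termination Criteria" and have three criteria:

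- **Criterion 1** covers patients with serious intercurrent events "who cannot continue to perform exercise during the trial".
- **Criterion 2** covers "Patients who underwent kidney transplantation or disappeared or died for various reasons during the trial".
- **Criterion 3** covers "Patients with poor compliance during the trial, unwilling to continue to exercise or requesting to withdraw from the trial for various reasons".

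Section 2.5 is the whole statistical plan. It names the software, descriptive statistics, a normality check, the chi-square test, a significance level of 0.05 and, for normally distributed quantitative data, "t-test is used for comparison between two groups", with a nonparametric test otherwise. It gives no analysis population and no method for missing values. Nothing in the protocol says whether measurement continues after exit.

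**The concern.** Randomisation makes the arms comparable only while the patients compared are those who were randomised. Section 3 puts events that belong to the exercise programme (inability to continue it, unwillingness to continue it, poor compliance) in the same list as death, loss and requested withdrawal. A control has no assigned exercise to abandon. An intervention patient with a serious infection who cannot exercise meets criterion 1, while a control with the same infection does not clearly do so. Poor compliance has no threshold and nobody is named to judge it, so that exit is also open to discretion.

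Patients who stop because of injury, an operation, infection or heart and lung failure plausibly do worse on grip strength, sit-to-stand, up-and-go and balance. Losing them mainly from one arm improves that arm's mean without any effect of Baduanjin. With 25 per arm, a few such losses matter, and every primary outcome is exposed. Values that are not collected at months 6 and 12 cannot be recovered later.

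**Working it through.** **No figure to reproduce.** The protocol gives no power calculation, standard deviation, expected exit rate or relation between exit and outcome. What follows is an illustration.

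**Inputs from the plan.** 25 per arm (section 2.2); two-sample t-test and P < 0.05 (section 2.5). Sidedness is not stated; two-sided is assumed.

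**Assumptions.** The outcome is standard normal in both arms, higher is better (timed tests reversed), and there is no true effect. Exit follows a latent score with correlation ρ to the outcome, and the lowest scorers exit. ρ is 0, 0.3, 0.5 or 0.7.

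**Approximate bias.** If a fraction d of an arm exits, the mean of those remaining shifts by

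ρ × φ(z_d) / (1 − d),

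where z_d is the d-quantile of the standard normal distribution and φ its density. The bias in the comparison is the intervention shift minus the control shift.

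- Five of 25 exit: d = 0.20, z = −0.842, φ = 0.280, and 0.280 / 0.80 = 0.350. Times ρ = 0.3, 0.5, 0.7 this is 0.105, 0.175, 0.245 SD.
- Two of 25 exit: d = 0.08, φ = 0.1487, and 0.1487 / 0.92 = 0.162. Five intervention against two control exits then gives (0.350 − 0.162) × ρ = 0.056, 0.094, 0.132 SD.

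**Simulation.** 100,000 trials per setting: remove the exits, then run the t-test.

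| Exits, intervention / control | Bias in SD at ρ = 0.3 / 0.5 / 0.7 | Two-sided type I error |
|---|---|---|
| 3 / 0 | 0.064 / 0.108 / 0.150 | 5.6 / 6.8 / 8.7% |
| 5 / 0 | 0.100 / 0.169 / 0.234 | 6.3 / 8.9 / 13.3% |
| 7 / 0 | 0.136 / 0.226 / 0.317 | 7.3 / 11.7 / 18.8% |
| 3 / 2 | 0.019 / 0.033 / 0.045 | 5.4 / 5.8 / 6.5% |
| 5 / 2 | 0.055 / 0.093 / 0.129 | 5.7 / 6.7 / 8.8% |
| 7 / 2 | 0.089 / 0.150 / 0.208 | 6.1 / 8.3 / 12.3% |

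At ρ = 0 the bias is 0 and the error 5.0% throughout. Independent repeats agree to within simulation error. False positives in favour of Baduanjin, nominally 2.5%, rise to about 5 to 13% with 5 / 0 exits and about 4 to 8% with 5 / 2.

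**Does baseline adjustment repair it?** With 5 / 0 exits tied to the later outcome and an assumed baseline-outcome correlation of 0.7 (40,000 runs), adjusting the remaining patients for baseline cuts the bias from 0.101 / 0.169 / 0.236 to 0.051 / 0.090 / 0.124 SD, about half. Only when exit depends on baseline alone does adjustment bring it to 0. The missing measurements therefore have to be collected.

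**Scale.** At 25 per arm, 80% power and two-sided 5%, the detectable difference is (1.960 + 0.842) × √(2/25) = 0.79 SD.

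**The case against.** **The exclusion is inferred.** The plan never says that patients who exit go unmeasured or unanalysed, and the schedule in section 2.2 has no exception. That is true. But the heading concerns leaving the trial, these reasons are listed with death and loss, and a t-test uses only patients with a value. The silence leaves the choice open until results are known.

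**The direction is assumed.** This stands in part. The prognostic argument is strongest for criterion 1; for patients who are merely unwilling, the documents offer nothing either way. If those who stop are fitter, the sign reverses: ρ = −0.3 with five intervention and no control exits gives −0.10 SD, against Baduanjin. Bias toward Baduanjin is a plausible risk, not a certainty.

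**Controls exit too.** Transplantation, death, loss and requested withdrawal are open to both arms, and poor compliance is not expressly confined to exercise. With five against four exits the bias is only 0.02 to 0.04 SD and the error about 5.2 to 6.9%. So the exits fall mainly, not only, on one arm, and the upper figures in the table need a marked imbalance.

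**The fix is incomplete.** Some patients will be unable to perform a physical test. If three of five exits stay unmeasured, the 3 / 0 row still leaves 0.06 to 0.15 SD. That is why a sensitivity analysis is needed; it is no reason not to measure the others.

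**Conclusion.** The concern holds and should be corrected. Followed as written, section 3 takes patients out of a randomised comparison after randomisation, mainly from one arm, for reasons tied to the assigned treatment, and nothing elsewhere in the plan puts them back.

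The size cannot be derived from the documents. Under the stated assumptions it runs from nothing (exit unrelated to outcome), through 0.05 to 0.13 SD (five against two exits), to 0.14 to 0.32 SD with a type I error of 7.3 to 18.8% (seven against none). Most of these values are small beside the detectable 0.79 SD, but they can produce a false positive result. The correlation may differ by outcome and may be weaker for bone density than for the performance tests. The plan as written would not show which case applies. Confidence is medium: the text is clear, but the exit rate and the prognosis of those who exit are unknown.

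**What to change.** Leave the clinical criteria for stopping exercise as they are, and change what follows from them.

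1. **Section 3.** State that stopping exercise under criterion 1, and poor compliance or unwillingness to exercise under criterion 3, do not end participation in the study.
2. **Follow-up.** Measure every randomised patient at months 6 and 12 unless consent is withdrawn, the patient dies or is lost, or the investigator judges a given test medically unsuitable. Record the reason.
3. **Section 2.5, primary analysis.** Analyse by assigned arm, using all available data from every randomised patient, with a stated method for missing values. One option is a repeated-measures mixed model with baseline included as an outcome, so that patients with no later value still contribute.
4. **Sensitivity analysis.** Shift missing intervention-arm values toward worse outcomes until the conclusion changes, and report that point.
5. **Compliance.** Define it numerically and keep the compliant subset as supportive only.
6. **Reporting.** Give exits, deaths and transplants by arm and reason.

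**Cost.** A short amendment to sections 3 and 2.5, with ethics committee approval under section 4.1. There are no new scheduled visits or procedures. Most patients still attend the dialysis centre; a few, such as those transplanted, may need a return visit. The estimated effect will be somewhat diluted by non-compliers. The change does most good if made before patients exit.

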4.1 Ethical Approval

This clinical research protocol complies with the relevant provisions of the Helsinki Declaration regarding the protection of subject rights. This protocol, written informed consent form, and materials directly related to the subjects must be submitted to the ethics committee for written approval before the study can be officially conducted. If this protocol has been revised during the clinical research implementation process, it must be submitted to the ethics committee for approval before implementation, and these changes cannot be implemented without the approval of the ethics committee, unless they are made to eliminate obvious and direct risks to the subjects. When such situations occur, they will be reported to the ethics committee. If important new information related to the study is found, the informed consent form must be modified in writing and submitted to the ethics committee for approval before obtaining the consent of the subjects again. Each clinical research center agrees that before the start of this research project, the ethics committee of the team leader unit shall review the research plan. The ethics committees of each sub center may choose to file or review it themselves. If necessary (such as serious adverse events or protocol violations), the ethics committees of each center shall convene a meeting in a timely manner for review and report the review conclusions to the ethics committees of other

centers.

